Total study population (n=128). CG (n=64) and IG (n=64) will be recruited consecutively during hospital admission post-surgery from April 2018 - March 2019. The inclusion and exclusion criteria will be the same as in study two.

Statistics

The sample size of this study (n=128) is based on a power calculation with an SD of 20; effect size 10 and power of 0,8. SD is based on similar studies on Head and Neck patients [48] and effect size on recommendations from EORTC [49], further the sample size is based on previous research in the Department of ORL H&N, Copenhagen University Hospital. To account for an expected dropout rate and non-recruitment rate of approximately 20% [50][51], the number of patients included in the study will be 160. Furthermore, based on the ratio between newly diagnosed patients and recurrences, we will stratify each study arm as follows; newly diagnosed (n=43) and recurrences (n=21).

Procedures

CG will receive standard care according to the Danish Health and Medicine Board's follow-up programme for HNC patients [52], which requires all patients have their physical, emotional, social and existential needs assessed by interview with a HCP, at three time-points post-treatment. At present this is done at the Dept. of ORL, H&N during the admission period post-surgery, two weeks and two months post-surgery, by a staff nurse who is a member of the rehabilitation team who perform nurse consultations. These consultations take place after the appointment with the surgeon. The nurse refers the patient to physical rehabilitation if needed.

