Quantitative outcomes: The primary outcome will measure the effect of the intervention by PRO quality of life and symptom questionnaire EORTC QLQ-H&N35. H&N35 is a 35-item questionnaire to be used with a core questionnaire[53]. The H&N module particularly measures oral pain, nutritional and voice problems. Patients will be asked to complete the EORTC QLQ-H&N35 at four time-points, 1) baseline (before randomisation) 2) between discharge and first follow-up in OPD 3) 7 days after first and 4) second post-surgical appointments – by telephone. Presence and severity of symptoms will be evaluated by MDASI-HN (MD Anderson Symptom Inventory) which is a multi-symptom patient-reported outcome measure for clinical and research use ([54]). MDASI-HN is a 28-item questionnaire which measures symptoms of HNC patients. Finally the patients physical activity level will be measured according to the Saltin-Grimby Physical Activity Level Scale, which

is a four-item questionnaire measuring the patients activity level [55]. MDASI-HN and Saltins will be used at four time-points – baseline (before randomization); before discharge; at first and second post-surgical appointment. Demographic and medical data (age, sex, diagnosis) will be registered at baseline and the types and number of multi-disciplinary referrals will be registered at each follow-up. The outcomes and items patients choose on the PCI will be registered. Finally the acceptance and adherence to the study will be assessed by registering the number of patients recruited and participating in the study and the attrition rate.

Qualitative outcomes: Qualitative interviews and focus group interviews will be carried out at the second post-surgical appointment to explore patient and HCP perspectives regarding the use of PCI. The interviews will be based on semi-structured interview guides. For the qualitative individual interviews, patients from IG (n= 15) will be recruited at the OPD, at the two-week appointment, from August to September 2018 and carried out October to November 2018. For the focus group interview, doctors and nurses (n=6-8) will be recruited at the Department from January - February 2019 and carried out March 2019.

Data and analysis

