The baseline demographic, medical data and number and types of referrals to multi-disciplinary team will be compared between the two trial arms using the chi-square test for categorical variables, the Student's t-test for normally distributed continuous variables, and the Mann-Whitney test for non-parametric variables. Descriptive data will be presented as means with standard deviations, medians with inter-quartile ranges or frequencies with percentage depending on the distribution of the variable. For the intervention group; feasibility, acceptance, adherence, attrition (and reasons) and safety will be calculated in mean and percentage. Data from the PRO questionnaires will be keyed in a database, compared across groups using SAS program to evaluate for statistical difference and effect size, by two-sample t-test. Analysis of covariance (ANCOVA) will be applied for comparisons of groups adjusted for, e.g. smoking and alcohol consumption status or sex.

Qualitative: The focus group interview and the individual interviews will be recorded digitally, transcribed verbatim and coded in the software program NVivo. Thematic analysis will follow a model where the transcriptions will be read and re-read, coded according to emerging themes, a clustering of themes and finally reaching a number of themes, which describes the patient's or HCP's experiences with the PCI in the new model of care [45]. Researcher triangulation will be applied.

A detailed project description for this part of the study will be developed.

Ethical considerations

Patients will receive oral and written information that participation is voluntary and that they may withdraw at any time without affecting treatment and care. Written informed consent will be obtained from patients participating at time of recruitment. The Regional Ethics Committee of the Capitol Region of Denmark has been approached regarding approval of the study. They have assessed this and deemed an approval unnecessary (Jr. no: 16036032)

The study has been approved by the Danish Data Protection Agency (RH-2017-264 ,I-Suite no: 05781) and will be sought registered at ClinicalTrials.com. The study will be carried out in accordance to the Helsinki Declaration and published according to Vancouver guidelines.

Clinical Perspectives

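### The primary outcome is the whole QLQ-H&N35 with no primary score or visit named, so the sample-size inputs (SD 20, difference 10, power 0.8) belong to no defined comparison

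*Protocol*

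**What the plan says.** Under Study three, Outcome measures, the protocol states: "The primary outcome will measure the effect of the intervention by PRO quality of life and symptom questionnaire EORTC QLQ-H&N35". It adds that "H&N35 is a 35-item questionnaire to be used with a core questionnaire" and that "The H&N module particularly measures oral pain, nutritional and voice problems". Completion is at four times. The first is baseline, before randomisation; the others are given as "2) between discharge and first follow-up in OPD 3) 7 days after first and 4) second post-surgical appointments".

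Under Statistics, the total of 128 "is based on a power calculation with an SD of 20; effect size 10 and power of 0,8". The SD is attributed to similar head and neck studies (reference 48), the difference to EORTC recommendations (reference 49), and the size also to earlier departmental research. No score or visit is attached to any of these. Alpha is not given. An allowance of about 20% raises the number to 160.

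Under Data and analysis, PRO data are "compared across groups using SAS program to evaluate for statistical difference and effect size, by two-sample t-test". Then: "Analysis of covariance (ANCOVA) will be applied for comparisons of groups adjusted for, e.g. smoking and alcohol consumption status or sex". Neither sentence names a score or a visit.

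The study hypothesis covers both short and long term symptom burden and quality of life. The aim of Study three puts symptom burden and quality of life last, as matters to explore. Neither narrows the primary outcome.

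**The concern.** A primary outcome has to be specific enough that two analysts, given the same data, would report the same primary result. Here they need not. One could take a pain score at the first post-baseline assessment, another a voice score at the last, and both would be following the text. The form is open too: level or change, and plain t-test or ANCOVA with covariates given only as examples.

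Two things are at stake:

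- **The primary claim.** Design and methods says allocation is blinded to neither investigator nor patients, and Procedures allows the main investigator to deliver the intervention consultations. Nothing in the protocol stops the primary score and visit from being settled once differences between arms can be seen.
- **The power statement.** An SD and a difference are properties of a particular score at a particular time. Without one, a reader cannot check whether 20 and 10 are suitable or which comparison has power 0.8.

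**Working it through.** **Inputs from the protocol.** Statistics: SD 20, difference 10, power 0.8, total 128 (64 per arm), 160 after about 20% loss. Design and methods: 1:1 allocation. Data and analysis: two-sample t-test. Alpha is not stated and is assumed to be two-sided 5%.

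**Step 1: reproduce the plan's figure.** Standardised difference d = 10/20 = 0.5.

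- Normal approximation: n per arm = 2 × (1.960 + 0.842)² / 0.5² = 62.8, so 63.
- t-based calculation: n per arm = 63.77, so 64 per arm and 2 × 64 = 128 in total. Power at 64 per arm is 0.801.
- Allowance for loss: 128 / (1 − 0.20) = 160.
- Check on alpha: two-sided 1% gives 95.1 per arm; two-sided 10% (equivalently one-sided 5%) gives 50.15. Two-sided 5%, or its one-sided 2.5% equivalent, returns 64.

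The arithmetic is right, for one comparison of two means.

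**Step 2: look for that comparison in the text.**

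| Section | Score named? | Visit named? |
|---|---|---|
| Study hypothesis and objective | No | No (short and long term) |
| Study three, Aim | No | No |
| Statistics | No | No |
| Outcome measures | No (whole module) | No (three post-baseline times) |
| Data and analysis | No | No |

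**Step 3: how far the stated power depends on the unnamed score.** The difference is held at 10 points, with a two-sided 5% t-test. SDs other than 20 are assumptions to show the range; the protocol does not give them.

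| SD | d = 10/SD | Power at 64 per arm | Analysed total for power 0.8 | Difference detectable with power 0.8 at 64 per arm |
|---|---|---|---|---|
| 15 | 0.667 | 0.96 | 2 × 37 = 74 | 7.5 |
| 20 | 0.500 | 0.80 | 2 × 64 = 128 | 10.0 |
| 25 | 0.400 | 0.61 | 2 × 100 = 200 | 12.5 |
| 30 | 0.333 | 0.46 | 2 × 143 = 286 | 15.0 |

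**Step 4: illustration if several comparisons share primary status.** Three is an assumed count, for example one score at the three post-baseline times.

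- Chance of at least one false positive with unadjusted 5% tests: 1 − 0.95³ = 0.143 under independence. In simulation (64 per arm, 100,000 runs) it was 0.134, 0.126 and 0.110 at correlations 0.3, 0.5 and 0.7.
- Bonferroni at 0.05/3: per-test power 0.66 at 64 per arm. Per-test power 0.8 needs 85.2, so 86 per arm and 172 analysed, or 172/0.8 = 215 recruited, against 128 and 160 planned.
- With d = 0.5 on all three (40,000 runs, same correlations): power for at least one significant result after adjustment is 0.91, 0.87 and 0.82; average per-test power under Holm is 0.74, 0.73 and 0.73.

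The last line shows that 128 could suffice for an any-scale claim but not for 0.8 on each scale. The protocol would have to say which is meant.

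**The case against.** The strongest reply is that more specification was promised. Data and analysis ends with: "A detailed project description for this part of the study will be developed". The sentence follows the qualitative paragraph, but Study two closes with a nearly parallel sentence that covers the whole of that study, so it may be meant for the whole trial. A statistical analysis plan may also exist. It is true that multiplicity rules and model details often sit there. But a promise defines nothing, and the protocol itself both declares the primary outcome and sizes the trial on it. Score and time are therefore a protocol-level matter.

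Other objections stand in part:

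- The SDs of 15, 25 and 30 have no basis in the protocol. They show sensitivity, not a shortfall. The source cited for SD 20 may concern a specific score; the protocol does not say.
- The three-test case is only an illustration, and its Bonferroni figures alone would give too dark a picture, which is why the any-scale and Holm figures are shown beside them.
- Reference 49 is titled for the Core 30, not the H&N35. The module is used alongside a core questionnaire, so citing core guidance is not in itself an error. It is a point to check.
- Figure 1 is not shown in the available copy. The statement that no score or visit is named covers the visible text.

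**Conclusion.** The concern holds and must be fixed. The protocol names a questionnaire where it should name an endpoint, and no visible section supplies the score, the visit or the form of comparison. The sample-size arithmetic is sound: 64 per arm, 128 analysed and 160 recruited all reproduce for a single test at an inferred two-sided 5%. No error in 128 is shown.

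What cannot be verified is that the primary comparison has power 0.8. At a 10-point difference it could lie anywhere from 0.96 to 0.46 over assumed SDs of 15 to 30. Followed literally, the analysis section leads to unadjusted tests across scores and visits in an open-label trial, with roughly 11% to 14% risk of a false positive for even three tests. The severity rests on the undefined endpoint, not on that illustration.

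**What to change.** Before any between-arm outcome comparison, issue a dated protocol change that:

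1. Names one primary H&N35 score, at the sponsor's choice, at one time point, or one pre-stated longitudinal contrast over the post-baseline times. It should also say whether level or change is compared and which of the t-test and ANCOVA is primary. The fourth assessment is one option: read as 7 days after the second appointment, it is the only one that follows all three nurse consultations.
2. States two-sided alpha 5%.
3. Gives the SD and difference for that score with their source, including whether reference 49 supports 10 points on an H&N35 score, and then confirms 128 or restates the power.
4. Makes all other scores and times secondary. If several scales stay primary, it states a multiplicity procedure such as Holm and whether power is per scale or for any scale.

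The deadline cannot be tied to unblinding, because allocation is open. The cost is a wording change with no new data collection. The downside is that other scores and visits can no longer carry the primary claim, and the stated power may look less favourable if the chosen score's SD exceeds 20 (0.61 at SD 25).

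### Interviews about the PCI with 15 intervention patients are placed before, or alongside, the final patient-reported assessments; stating that they follow those assessments removes a small, avoidable one-arm contact

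*Protocol*

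**What the plan says.** All of the timing stands in the Outcome measures section of Study three.

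- **Interviews.** The protocol says: "Qualitative interviews and focus group interviews will be carried out at the second post-surgical appointment". The individual interviews explore how patients see the use of the PCI. On who is interviewed: "patients from IG (n= 15) will be recruited at the OPD". Recruitment falls in August and September 2018, at the two-week visit, and the interviews fall in October and November 2018. No interview of control patients is described.
- **Focus group.** "For the focus group interview, doctors and nurses (n=6-8) will be recruited at the Department" in January-February 2019, and the group is held in March 2019. It involves staff only.
- **Primary outcome.** "The primary outcome will measure the effect of the intervention by PRO quality of life and symptom questionnaire EORTC QLQ-H&N35". It is completed at baseline, between discharge and the first outpatient follow-up, and then "3) 7 days after first and 4) second post-surgical appointments – by telephone".
- **Other questionnaires.** MDASI-HN and Saltin-Grimby are taken at baseline, before discharge, and "at first and second post-surgical appointment".

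Elsewhere in Study three, Design and methods says that neither investigators nor patients are blinded. Procedures places the nurse consultations during admission, at two weeks and at two months after surgery, and lists the six steps of the intervention. A research interview is not one of them. Data and analysis plans a two-sample t-test and ANCOVA, makes no separate provision for interviewed patients, and announces a detailed project description still to be written for this part of the study.

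**The concern.** A semi-structured conversation about the PCI directs the patient's attention to the intervention and to his or her own symptoms. As written, it takes place in one arm only, about a week before the final H&N35 and on the same day as the final MDASI-HN and Saltin-Grimby. The patients know their allocation and rate themselves. The interview is research contact that would not exist if the PCI were used routinely, yet any effect it has on the ratings would be counted as an effect of the PCI.

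The direction is not known. Attention might improve ratings, and talking about problems might raise symptom reporting. In the first case the arm difference is inflated; in the second it is reduced by the same amount. At stake is a small contamination of the last comparison that the schedule could avoid at almost no cost.

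**Working it through.** **Inputs.** From Statistics: SD 20, target difference 10, power 0.80, 64 per arm (128 in total), 160 after allowance for about 20% loss. From Outcome measures: 15 interviewed patients, all in the intervention arm. Assumptions, because the protocol gives no figure: two-sided alpha of 0.05, and a mean shift of 2, 5 or 10 points in each interviewed patient.

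**The plan's own figure.** Normal approximation: n per arm = 2 × (1.960 + 0.842)² × 20² / 10² = 62.8, so 63. The t-test version gives 63.8, so 64 per arm and 128 in total. Allowing for 20% loss: 128 / 0.80 = 160. The sample size is reproduced and is not in question.

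**Share of the arm.** 15/64 = 23.4%. If all 160 are analysed, 15/80 = 18.8%. The control share is 0%.

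**Shift in the arm mean.** Shift = (15/n) × assumed shift per interviewed patient. Standard error of the difference = 20 × √(2/n), which is 3.54 for n = 64 and 3.16 for n = 80. With d = shift / standard error, the false-positive rate is 1 − Φ(1.96 − d) + Φ(−1.96 − d).

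| Assumed shift per interviewed patient | Arm-mean shift, n = 64 | False-positive rate, n = 64 | Arm-mean shift, n = 80 | False-positive rate, n = 80 |
|---|---|---|---|---|
| 2 | 0.47 | 5.2% | 0.38 | 5.2% |
| 5 | 1.17 | 6.3% | 0.94 | 6.0% |
| 10 | 2.34 | 10.2% | 1.88 | 9.1% |

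Against the 10-point target, the shifts for n = 64 are 5%, 12% and 23%.

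**The calendar.** Take two months as 61 days, so the two-month visit falls 61 − 14 = 47 days after the two-week visit at which interviewees are recruited.

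- Recruited 14 August: visit on 30 September. Anyone recruited on 1-14 August therefore has the visit before the interview window opens on 1 October.
- Recruited 7 August: visit on 23 September and telephone H&N35 on 30 September. For the first week of August the last H&N35 is also over before the window opens.
- Recruited 30 September, the latest date: visit on 16 November and telephone H&N35 on 23 November, still inside the window.

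If recruitment is even over the 61 days of August and September (assumption), 15 × 14/61 = 3.4, so about 3 to 4 of the 15 cannot be interviewed at the visit. The dated window leaves room for all 15 interviews to follow the last H&N35.

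**After the change.** None of the 15 is interviewed before the final assessment, so the interview contributes 0 to the arm difference. The 128 and 160 are unchanged.

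**The case against.** The strongest case on the other side is that this is a loose sentence and not a demonstrated bias.

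- **The dates do not match the sentence.** The interview window excludes the visit for patients recruited in early August, and the same sentence puts the staff focus group at a patient appointment although that group is held once, in March 2019. This stands: a reader might infer that all 15 are interviewed a week before the last H&N35, and the protocol's own dates do not support that. The sentence is nevertheless the only statement of timing relative to the assessments, and most recruits could still be interviewed at the visit.
- **The size is assumed throughout.** The 10-point case credits one conversation with the full difference the trial is powered for. The false-positive figures also suppose that three consultations do nothing while one interview about them does something. This stands. At 2 points the effect is negligible.
- **The direction is open.** A reader might infer that the interview is supportive contact that favours the intervention. The protocol describes it only as exploring perspectives on the PCI.
- **The larger attention difference lies elsewhere.** A reader might infer that rescheduling would remove one-sided attention from the trial. It would not: the six-step consultations, with accompaniment to the surgeon, are part of the intervention and remain. So does the knowledge, from two weeks on, that an interview is coming.
- **Only one assessment is touched.** It is the last of three after baseline, and the protocol does not name it as the sole primary time point.
- **Convenience and later detail.** Interviewing at an existing visit spares the patient a contact, and the announced project description could settle the logistics. Both are fair, but neither gives a reason for placing the interview before the questionnaires.

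The timing of the last H&N35 could also be read as the second appointment itself. Interview and questionnaire would then share a visit with no order fixed, and the same clarification would be needed.

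**Conclusion.** The point holds as a minor improvement. As written, the schedule puts a research contact in one arm before the last H&N35, and on the same day as the last MDASI-HN and Saltin-Grimby in unspecified order, in an unblinded trial with self-reported outcomes. For assumed shifts of 2 to 5 points per interviewed patient, the arm mean moves by about 0.4 to 1.2 points and the false-positive rate stays at about 5-6%. A 10-point shift would be needed to reach 1.9-2.3 points and 9-10%. The likely bias is therefore small against the 10-point target.

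These figures rest on SD 20, 64 to 80 analysed per arm, an assumed two-sided alpha of 0.05, and all 15 interviews preceding the assessment, which the calendar makes an upper case. The documents do not show that a bias would occur or which arm it would favour. The staff focus group is not affected.

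**What to change.** In Outcome measures, qualitative outcomes, replace the timing of the individual interviews with a statement that each takes place after that patient's final H&N35, MDASI-HN and Saltin-Grimby have been completed. Give the focus group its own sentence with its March 2019 date. The announced project description for the qualitative part should repeat the rule.

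The October-November 2018 window can stay, and for patients recruited in early August it already requires an interview after the visit. The last telephone H&N35 can be used to arrange the interview. Sample size, analysis, number of interviews and interview content do not change. The cost is that up to 15 patients need an interview contact separate from the clinic visit.

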Life as it was prior to the disease and treatment cannot be the same afterwards, yet prevention of sequela could give patients better QoL long term. Therefore, there is a need to prevent or alleviate symptoms and the early and late negative effects of the disease and its treatment. Symptoms that could lead to sequela need to be assessed and managed early by referral to specialist follow-up i.e. speech-language pathologist, physio-and occupational therapists, dietician, clinical nurse specialist and psychologist [33][34][35]. To a greater extent, patients with HNC come from backgrounds of short education and manual labour, which place them at risk for health disparity [36][37][38]. The type and quality of decision-making tools used to assess health and rehabilitation needs are important to consider in patients with low health literacy [39]. Acknowledgment of the importance of patient-involvement in needs assessments using Patient Reported Outcomes (PRO) is growing. However present PRO questionnaires have certain limitations. Firstly, they have been developed for research purposes, therefore little is known about how these can be applied in the clinical setting to obtain the patient's information on the symptoms experienced [40]. Secondly, PRO questionnaires do not incorporate needs assessments [40]. Finally, there is currently, a lack of knowledge

regarding which type of decision making assessment tool would be optimal in patients with short education and low health literacy.

Study hypothesis and objective

The study's *hypothesis* is that a disease-specific patient-reported needs assessment tool integrated in the clinical management of HNC will increase patient involvement in decision making, control the short and long term symptom burden and improve short and long term health related quality of life (HRQoL) in HNC patients, primarily surgically treated. The *purpose* of the study is to investigate whether a systematic patient reported needs and concerns assessment integrated prior to and during consultations with health care professionals (HCP), is feasible and safe, and will improve patient involvement in decision making during the consultation. Further, whether patient involvement will result in increased referral to the multi-disciplinary team and ultimately reduce the symptom burden, improve physical, mental and social wellbeing and global HRQoL.

Study designs and methods

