The focus group interview and the individual interviews will be recorded digitally, transcribed verbatim and coded in the software program NVivo. Thematic analysis will follow a model where the transcriptions will be read and re-read, coded according to emerging themes, a clustering of themes and finally reaching a number of themes, which describes the patient's and nurses experiences with nurse-patient interactions [45]. Observations will be recorded as short field notes during observations and following this expanded as notes in a text-file. The field notes will follow the same analytic process as the interviews. Researcher triangulation will be applied.

A detailed project description for this part of the study is attached (Appendix I)

Study three – Randomized controlled trial

Aim

To evaluate the safety and effect of the PCI integrated in clinical practice. Specifically, to investigate whether patients and Health Care Professionals (HCP) find the PCI applicable and useful in assessing and managing care and rehabilitation needs. Furthermore, whether patients are referred more often to multi-disciplinary follow-up, which types of follow-up and whether the new needs assessment and decision-

making tool improves the interaction between HCPs and patients. Lastly, to explore whether patients experience a reduced symptom burden and improved HRQoL.

Linguistic and cross cultural validation of the PCI and Development of an IT-solution

Prior to the RCT, a linguistic and cross cultural validation of the PCI and development of an IT-solution within the context of a head and neck department in Denmark will be carried out. The PCI is a 57 item solution, where patients can select a range of items related to functional, emotional, social and existential areas [46] using touch screen buttons, which allows the patients to choose the items, they wish to discuss with the HCP. This enables the patient to express their concerns and symptoms and choose those items, they find important and meaningful to discuss. The PCI includes a brief electronic version of the University of Washington Quality of Life Questionnaire (UW-QoL), which aids the HCP in addressing needs that the patient may not be attentive to [41].

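### Attrition with reasons, and safety, are to be summarised for the intervention group only, in an unblinded two-arm trial that names safety as an aim

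*Protocol*

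**What the plan says.** Safety appears in both statements of intent. The overall purpose asks whether the assessment "is feasible and safe, and will improve patient involvement in decision making during the consultation", and the aim of Study three opens: "To evaluate the safety and effect of the PCI integrated in clinical practice". The design is two-arm, randomised 1:1, with neither investigator nor patients blinded. The primary outcome is a patient-reported questionnaire.

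Under Outcome measures, acceptance and adherence are to be assessed by "registering the number of patients recruited and participating in the study and the attrition rate". No arm is named there, and reasons for leaving are not mentioned. That section lists no safety measure.

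Under Data and analysis, one sentence restricts the summary to one arm: "For the intervention group; feasibility, acceptance, adherence, attrition (and reasons) and safety will be calculated in mean and percentage". The sentences around it take both arms. Of referrals the plan says "number and types of referrals to multi-disciplinary team will be compared between the two trial arms", and of the questionnaires, "Data from the PRO questionnaires will be keyed in a database, compared across groups using SAS program to evaluate for statistical difference".

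On numbers, Population and recruitment states: "CG (n=64) and IG (n=64) will be recruited consecutively during hospital admission post-surgery". Statistics then raises the total to 160, citing an "expected dropout rate and non-recruitment rate of approximately 20" per cent.

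**The concern.** The sentence groups five items under one restriction, and they are not alike. Feasibility and acceptance of the PCI, and adherence to it, exist only where the PCI is used. Patients can leave either arm, and adverse outcomes after surgery can occur in either arm.

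Two things are at stake. First, patients know their allocation and report the primary outcome themselves, and contact differs by arm: intervention patients are accompanied to the surgeon's appointment, while controls see the nurse after it. Reasons for leaving could plausibly differ. If reasons are tabulated for one arm only, a reader can see how many left each arm but cannot judge whether the losses are of the same kind. Second, an intervention-arm safety percentage cannot by itself separate an effect of the PCI from the ordinary course after surgery.

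**Working it through.** **Step 1. The plan's own figures.** Inputs from Statistics: SD 20, difference 10, power 0.80. Alpha is not stated there; two-sided 0.05 is assumed. The normal approximation, 2 × (1.96 + 0.84)² × (20/10)², gives 63 per arm. The t-test version gives 63.77, so 64 per arm and 128 in total, as stated. Allowing for 20%: 128 / (1 − 0.20) = 160, also as stated. The point made here does not depend on these figures; they supply only the arm sizes, 64, or 80 if all 160 are randomised 1:1.

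**Step 2. What is and is not available for controls.**

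| Item | Intervention | Control |
|---|---|---|
| Number lost | Calculated (Data and analysis) | Can be derived from the attrition registered for the study (Outcome measures) |
| Reasons for loss | Calculated | Not planned |
| Safety summary | Calculated | Not planned |
| Symptom and quality-of-life scores | Compared between arms | Compared between arms |
| Referrals | Compared between arms | Compared between arms |

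**Step 3. Counts alone.** Suppose 80 per arm and 20% lost overall, which is 32 of 160. If 8 leave the intervention group, 32 − 8 = 24 controls left (10% against 30%). If 24 leave it, 8 controls left (30% against 10%). The overall rate together with the intervention-group rate therefore gives the control count by subtraction. It does not give the reasons.

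**Step 4. Leavers without a planned summary of reasons.** Control leavers = n × dropout, with the same dropout in both arms.

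| Assumed dropout | n = 64 per arm | n = 80 per arm |
|---|---|---|
| 5% | 3.2 | 4 |
| 10% | 6.4 | 8 |
| 20% | 12.8 | 16 |

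Under equal loss this is half of all leavers. The dropout rates are assumptions, because the protocol's 20% combines dropout with non-recruitment.

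**Step 5. Precision of a by-arm safety difference.** 95% half-width = 1.96 × √(2p(1 − p)/n), with the same event rate p assumed in both arms. At p = 0.20 and n = 64: 1.96 × √(0.32/64) = 1.96 × 0.0707 = 13.9 points.

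| Assumed event rate | n = 64 per arm | n = 80 per arm |
|---|---|---|
| 5% | ±7.6 | ±6.8 |
| 10% | ±10.4 | ±9.3 |
| 20% | ±13.9 | ±12.4 |
| 30% | ±15.9 | ±14.2 |

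The protocol gives no safety event rate, so these too are assumptions. They show that such a comparison could only be descriptive.

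**The case against.** The strongest reply concerns safety. The aim speaks of the safety of the PCI, and only one arm receives the PCI, so safety can be read as a property of the tool, to be described alongside feasibility. The intervention is a nurse consultation aid, and harm in the form of worse symptoms or quality of life is already compared between arms through the questionnaires. No safety measure is named, so asking for safety by arm risks asking for a table of an undefined quantity, and recording safety events in controls is work that a wording change does not cover.

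Much of this stands. A reader might infer that the trial compares no harm between arms, or that a one-arm safety summary is an error in itself. The documents do not support either: the questionnaire comparison covers part of harm, and the aim allows the narrower reading. What remains is that the protocol lists safety separately from the questionnaire data and gives it no comparator. The remedy can reach only those safety items that are recorded in both arms, and they have to be named.

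On attrition, the reply is that the overall rate is registered without an arm limit, that the sentence does not say *only*, and that disposition tables by arm are often left to a statistical analysis plan, which was not available here. A reader might infer that control losses will go uncounted; that would be wrong, as Step 3 shows. But naming one arm goes further than leaving the matter open, and nothing in the protocol provides the control-arm reasons.

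**Conclusion.** The point holds in a limited form. As written, the analysis section yields reasons for leaving and a safety summary for the intervention group alone, so the nature of any differential loss cannot be properly judged and the safety percentage has no comparator. The attrition part is the firmer of the two. The safety part is limited to whatever items are recorded, since none is specified.

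The effect is on interpretation. No sample size, power or primary estimate changes, and nothing here shows that the primary comparison is biased. The size is about 3 to 13 control leavers at 64 per arm, or 4 to 16 at 80, without a planned summary of reasons. This assumes equal loss of 5% to 20%; with unequal loss the control share could be smaller or larger than half.

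**What to change.** In Data and analysis, keep feasibility and acceptance of the PCI, and adherence to it, as intervention-group summaries. Report attrition after randomisation by randomised arm, giving numbers, time-point and reasons. In Outcome measures, add *in each arm* to the attrition rate so that the two sections agree.

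For safety, state which items are used, collect them in the same way in both arms, and present them by arm with the comparison labelled descriptive.

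The attrition change costs little: the wording, and one reason-for-leaving field for controls if it is not already collected. Some patients will give no reason. The safety change costs more, because the same recording must be done in controls, and the comparison will be imprecise (about ±14 points at 64 per arm for an assumed 20% event rate). No extra patients, visits or questionnaires are needed for the attrition change. For safety, the burden depends on the items chosen.
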